8.7 Down-Titration Phone Call

- Recording of AEs

The Down-Titration Phone Call at the end of the Down-Titration Period is mandatory.

Down-titration is not applicable to subjects who transition to another BRV study or a managed access program or similar type of program or who convert to commercial BRV (if, when, and where available).

8.8 Final Visit

- Vital signs
- Weight
- Physical examination
- Neurological examination
- ECG (mandatory, except if the FV follows an EDV where ECG results were normal)
- IVRS call
- DRC retrieved
- Recording of seizures
- Laboratory safety assessments (mandatory, except if the FV follows an EDV where laboratory results were normal): hematology, blood chemistry, urinalysis, and urine pregnancy test (if applicable)
- Recording of AEs
- Suicidality assessment (C-SSRS)

- Medical procedures
- Concomitant AED
- Concomitant non-AED
- Drug return/accountability
- End of study status

The FV is not applicable to subjects who transition to another BRV study or a managed access program or similar type of program or who convert to commercial BRV (if, when, and where available).

9 ASSESSMENT OF EFFICACY

Efficacy variables will be assessed using the seizure count information recorded on the DRC.

At each visit, the subject will receive a DRC, to be filled in on days on which a seizure occurs, and to be returned at the next visit. No DRC will be dispensed at the UV or the FV.

The date and the number (where possible) of epileptic seizures will be recorded on the DRC, as well as the type of seizure (according to individual description of seizures), occurrence of clusters, intake of concomitant AEDs, undesirable events with start and end dates, healthcare provider consultations not foreseen per protocol, and changes in concomitant medication, if applicable.

The written information will be discussed with the subject at each visit in order to ensure completeness and accuracy. As a result of the discussion, the Investigator will assess the seizures according to the ILAE codes and record the seizure types and frequency on the CRF; he/she will also confirm the presence of AEs (if applicable). The concomitant medication changes, healthcare provider consultations not foreseen per protocol, and AEs will be reported by the Investigator on the specific pages of the CRF.

The DRC will be considered as source documentation. The subject should be educated to complete the DRC on all days with seizures (eg, when taking evening tablets). Substantial noncompliance with diary completion (seizures recording) may result in subject discontinuation from the study at any time by the Investigator or the Sponsor.

9.1 Additional efficacy and pharmacoeconomic assessments

9.1.1 QOLIE-31-P scores

The QOLIE-31-P - Version 2.0 (see Section 16.1) will be used to evaluate the HRQoL of study subjects (Cramer and Van Hammée, 2003).

The QOLIE-31-P is an adaptation of the original QOLIE-31 instrument (Cramer et al, 1998) that includes 30 items grouped into 7 multi-item subscales: seizure worry (5 items), overall quality of life (2 items), emotional well-being (5 items), energy/fatigue (4 items), cognitive functioning (6 items), medication effects (3 items), social function (5 items), and a health status item. The subscale scores, the total score, and the health status item score are calculated according to the scoring algorithm defined by the author, with scores ranging from 0 to 100 and higher scores indicating better function. In addition to these 31 items, the

QOLIE-31-P contains 7 items assessing the degree of “distress” associated with the topic of each subscale (ie, distress items) and 1 item asking about the relative importance of each subscale topic (ie, prioritization item). The QOLIE-31-P will be completed by subjects who are able to complete the assessments on their own, during the first 2 years at the FEV, YEV, Last Evaluation Period Visit, and EDV.

9.1.2 Socio-professional data

Socio-professional data, such as highest level of education, current professional status, housing status, regular assistance, and ability to drive, will be collected at the YEV, Last Evaluation Period Visit, and EDV during the first 2 years.

9.1.3 Medical procedures

Data on medical procedures (surgery, therapeutic and/or diagnostic, hospitalizations) undertaken during the study will be collected and recorded in the CRF. Electrocardiograms specific to this study will not be recorded on the medical procedures page of the CRF, but in the modules specifically designed for this purpose. Medical procedures will be recorded at the EV, FEV, MEV, YEV, Last Evaluation Period Visit, EDV, and FV during the entire study, but only the first 2 years of recording will be included in the outcome evaluation.

9.1.4 Healthcare provider consultations not foreseen by the protocol

At the FEV, MEV, YEV, Last Evaluation Period Visit, and EDV, healthcare provider consultations not foreseen by the protocol will be recorded in the CRF. It will include the type of provider (general practitioner, specialist physician, nurse), the site of care (office-private, office-hospital, home, emergency room), and the reason leading to the consultation. At the EV, data will be obtained from the last visit of the previous study, N01358 or N01258, and do not need to be recorded on the CRF for this study. Healthcare provider consultations not foreseen by the protocol will be recorded for the first 2 years.

9.1.5 Hospital stays

At the FEV, MEV, YEV, Last Evaluation Period Visit, and EDV, data on hospital stays will be collected in the CRF. It will include the reason leading to the hospitalization, the admission ward, transfers, and length of stay. At the EV, data will be obtained from the last visit of the previous study, N01358 or N01258, and do not need to be recorded on the CRF for this study. Hospital stays will be recorded for the first 2 years.

10 ASSESSMENT OF SAFETY

10.1 Adverse events

10.1.1 Definition of adverse event

An AE is any untoward medical occurrence in a patient or clinical investigation subject administered a pharmaceutical product which does not necessarily have a causal relationship with this treatment. An AE can therefore be any unfavorable and unintended sign (including an abnormal laboratory finding), symptom, or disease temporally associated with the use of a medicinal (investigational) product, whether or not related to the medicinal (investigational) product.

In order to ensure complete safety data collection, all AEs occurring during the study (ie, after signing the Informed Consent form), including any pretreatment and posttreatment periods required by the protocol, must be reported in the CRF even if no investigational product was taken but specific study procedures were conducted. This includes all AEs not present prior to the initial visit and all AEs which recurred or worsened after the initial visit.

Signs or symptoms of the condition/disease for which the investigational product is being studied should be recorded as AEs only if their nature changes considerably or their frequency or intensity increases in a clinically significant manner as compared to the clinical profile known to the Investigator from the subject's history or the Baseline Period.

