6.3 Withdrawal criteria

Subjects are free to withdraw from the study at any time, without prejudice to their continued care. Subjects who have signed an additional Informed Consent form for DNA analysis may withdraw their consent to the DNA analysis at any time and may continue their participation in the N01379 study.

Investigators should attempt to obtain information on subjects, in case of withdrawal or discontinuation.

For subjects considered as lost to follow-up, the Investigator should make an effort (at least 1 phone call and 1 written message to the subject), and document his/her effort (date and summary of the phone call and copy of the written message in the source documents) to complete the final evaluation.

The Investigator should make an effort, and document his/her effort, to complete the EDV and preferably also the FV.

All results of these evaluations and observations, together with a narrative description of the reason(s) for removing the subject, must be recorded in the source documents. The Case Report Form (CRF) must document the primary reason for withdrawal or discontinuation.

Investigators should contact the Medical Monitor whenever possible to discuss the withdrawal in advance.

When possible, the study medication will be progressively down-titrated in the case of discontinuation. During the Down-Titration Period, the dose may be decreased in steps of a maximum of 50mg/day on a weekly basis. A last down-titration step at 20mg/day for 1 week

will be included prior to the Posttreatment Period. The Down-Titration Period will be followed by a Posttreatment Period of a minimum of 2 weeks and a maximum of 4 weeks.

Stopping rules and discontinuation criteria for individual subjects may be, for example:

- Withdrawal for safety reasons by the Investigator: occurrence of status epilepticus, appearance of a more severe type of seizure, significant increase in liver enzymes, and any other significant safety reason, or if the subject develops an illness that would interfere with his/her continued participation.
- Subject and/or Investigator does not think that the investigational drug is effective (ie, lack or loss of efficacy).
- Lost to follow-up.
- Withdrawal of consent for personal reasons not related to AEs or lack/loss of efficacy.
- Other reason that has to be specified in the CRF.
- There is confirmation of a pregnancy during the study, as evidenced by a positive pregnancy test.

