10.2 Serious adverse events

10.2.1 Definition of serious adverse event

Once it is determined that a subject experienced an AE, the seriousness of the AE must be determined. An SAE must meet 1 or more of the following criteria:

- Death
- Life-threatening
(Life-threatening does not include a reaction that might have caused death had it occurred in a more severe form.)
- Significant or persistent disability/incapacity
- Congenital anomaly/birth defect (including that occurring in a fetus)
- Important medical event that, based upon appropriate medical judgment, may jeopardize the patient or subject and may require medical or surgical intervention to prevent one of the other outcomes listed in the definition of serious
(Important medical events may include allergic bronchospasm requiring intensive treatment in an emergency room or at home, blood dyscrasias that do not result in inpatient hospitalization, or the development of drug dependency or drug abuse.)
- Initial inpatient hospitalization or prolongation of hospitalization
(A patient admitted to a hospital, even if released on the same day, meets the criteria for the initial inpatient hospitalization. An emergency room visit that results in admission to the hospital would also qualify for the initial inpatient hospitalization criteria. However, emergency room visits that do not result in admission to the hospital would not qualify for this criteria and, instead, should be evaluated for 1 of the other criteria in the definition of serious [eg, life-threatening adverse experience, important medical event].
Hospitalizations for reasons not associated with the occurrence of an AE [eg, preplanned surgery or elective surgery for a pre-existing condition that has not worsened or manifested in an unusual or uncharacteristic manner] do not qualify for reporting. For example, if a subject has a condition recorded on his/her medical history and later has a preplanned surgery for this condition, it is not appropriate to record the surgery or hospitalization as an SAE since there is no AE upon which to assess the serious criterion. Please note that, if the pre-existing condition has worsened or manifested in an unusual or uncharacteristic manner, this would then qualify as an AE and, if necessary, the seriousness of the event would need to be determined.)

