10.4 Anticipated serious adverse events

The following list of Anticipated SAEs has been identified, as these events are anticipated to occur in the population studied in this protocol at some frequency that is independent of drug exposure: convulsion. This original list will remain in effect for the duration of the protocol.

The list does not change the Investigator's obligation to report all SAEs (including Anticipated SAEs) as detailed in Section 10.2.2.

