11.2.2 General summaries of TEAEs

Pre-treatment AEs will be provided in a subject data listing; no summaries of pre treatment AEs are planned.

An overall summary of AEs will provide the overall number of TEAEs and the numbers and percentages of subjects with at least 1 TEAE, with a TEAE that led to permanent discontinuation of study drug, with a drug-related TEAE, with a severe TEAE, with a treatment-emergent SAE, and with a drug-related treatment-emergent SAE. The number and percentage of subjects who died will also be summarized. This summary will be provided for all subjects in the Safety Analysis Set and also by subgroup for geographic region and seizure type.

The following summaries of TEAEs will be provided by MedDRA SOC and PT. All summaries are for the combined Evaluation, Down-Titration, and Post-Treatment Periods unless otherwise indicated.

Overall Incidence Summaries

- Incidence of TEAEs
- Incidence of TEAEs by 3-month time interval
- Incidence of TEAEs by study period (Evaluation, Down-Titration, Post-Treatment)
- Incidence of TEAEs for TEAEs occurring in at least 5% of subjects
- Incidence of TEAEs by 3-month time intervals for TEAEs occurring in at least 5% of subjects overall
- Incidence of non-serious TEAEs occurring in at least 5% of subjects

The incidence of TEAEs occurring in at least 5% of subjects will be summarized overall as noted above and also by subgroup for geographic region, seizure type, and randomized treatment from the previous double-blind study.

A subject is included in a 3-month interval if the subject was receiving BRV at any time during that interval based on their duration of exposure to BRV (eg, a subject with exposure for 91 days is included in the time interval for Months 1-3 and Months 4-6). Summaries of AEs by 3-month intervals will include all subjects who are classified into each time interval as defined above. TEAEs which had onset prior to or on the date of the last dose of BRV) are included in summaries by 3-month time intervals.

Maximum Intensity and Causality

- Incidence of TEAEs by maximum intensity
- Incidence of drug-related TEAEs

Serious Adverse Events

- Incidence of treatment-emergent SAEs

Discontinuations due to TEAE

- Incidence of TEAEs leading to permanent discontinuation of study drug

TEAEs of interest

AEs of interest will be identified based on MedDRA search criteria, which are documented outside of the SAP. The following summaries will be provided for AEs of interest:

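### Protocol 10.1.1 makes no exception for serious seizures, so a seizure within the subject's known profile that leads to admission need not be recorded as an SAE

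*Protocol*

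**What the plan says.** - **Protocol 10.1.1** restricts AE recording for manifestations of the disease under study. They "should be recorded as AEs only if their nature changes considerably or their frequency or intensity increases in a clinically significant manner", and the yardstick is "as compared to the clinical profile known to the Investigator from the subject's history or the Baseline Period". Seriousness is not mentioned.
- **Protocol 10.2.1** sets the order of assessment: "Once it is determined that a subject experienced an AE, the seriousness of the AE must be determined". It excludes from reporting "Hospitalizations for reasons not associated with the occurrence of an AE", with planned or elective surgery as the examples. Conversely, "if the pre-existing condition has worsened or manifested in an unusual or uncharacteristic manner, this would then qualify as an AE".
- **Protocol 10.3** describes an SAE as an AE that the investigator has classed as serious.
- **Protocol 10.4** gives the list of anticipated SAEs on the ground that "these events are anticipated to occur in the population studied in this protocol at some frequency that is independent of drug exposure: convulsion". It adds that the list leaves unchanged the duty under 10.2.2 to report every SAE, anticipated ones included.
- **Protocol 4.1.1** names occurrence of an SAE as one of three primary safety variables.
- **SAP 11.2.2** plans "Incidence of treatment-emergent SAEs" by system organ class and preferred term. Its overall AE summary, which includes SAEs, is also given by geographic region. It has no rule for seizure events.
- **Protocol 9.1.5** collects hospital stays with their reason for the first 2 years. **Protocol 9.1.3** collects medical procedures, including hospitalizations, for the whole study.

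**The concern.** Seizures are the disease under study, so most should stay out of the AE data. The restriction in 10.1.1, however, works on how usual the event is for that subject, not on how severe its consequences are. In a largely refractory population, a usual seizure can still end in admission. If such an event is stopped at the AE step, it never reaches the seriousness step and is missing from a primary safety variable.

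Section 10.4 can lead another site to report the same event. The SAE percentage would then mix two recording practices. Because the SAE summary is also shown by region, a difference in practice could look like a difference in safety.

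**Working it through.** The documents state no figure on this point and the study has no sample size calculation, so the check is mainly a reading of the sections in sequence.

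**1. Follow one event through the text.** Take a seizure of the subject's usual type, at the usual frequency and intensity, that leads to admission.

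| Step | Section | Result on a literal reading |
|---|---|---|
| Is it an AE? | 10.1.1 | No: nothing exceeds the known profile |
| Is it serious? | 10.2.1 | Not reached: the event must first be an AE |
| Is it reported immediately? | 10.3 | No: an SAE is an AE classed as serious |
| Is it in the SAE table? | SAP 11.2.2 | No: there is no AE record to tabulate |

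**2. Does 10.2.1 bring it back?** Admission is one of its criteria, even with discharge the same day, but it applies only to an event already accepted as an AE. The text on pre-existing conditions again requires worsening or an unusual presentation. An investigator may judge that an admission shows greater intensity, but no section says so.

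**3. Does 10.4 bring it back?** Two readings are open:
- *Nested:* the anticipated SAEs are convulsions that passed 10.1.1 and were then found serious. This fits the reference to 10.2.2.
- *Wide:* convulsions occurring at a background frequency unrelated to the drug include those within the subject's profile, and all SAEs must be reported.

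The text does not choose between them.

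**4. Direction.** The literal reading only removes events. The shift in SAE incidence is

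shift = (subjects whose only events meeting a 10.2.1 criterion are in-profile seizures) / (subjects in the Safety Population).

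It is zero or positive, and the documents do not give the numerator.

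**5. Scale only.** Text deleted by Protocol Amendment 3 gave convulsion SAEs in two other open-label follow-up studies as 1.8%. Planned enrolment is 650 to 720 from N01358 plus up to 100 from N01258, so at most 720 + 100 = 820.
- At 1.8%: 0.018 × 650 = 11.7 and 0.018 × 820 = 14.8, or about 12 to 15 subjects.
- At an assumed 0.5%: 0.005 × 650 = 3.25 and 0.005 × 820 = 4.1, or about 3 to 4 subjects.
- At an assumed 5%: 0.05 × 650 = 32.5 and 0.05 × 820 = 41, or about 33 to 41 subjects.

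These are counts of subjects with convulsion SAEs at each rate. They do not show how many such subjects would be missed.

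**The case against.** The strongest reply is that the sections are nested, not opposed. Section 10.4 says convulsion and nothing about the subject's usual seizures, refers back to 10.2.2, and adds no class of reportable event. That is a fair reading. A reader might infer that 10.1.1 and 10.4 flatly contradict each other; the documents do not support this, and what they leave is an ambiguity. But the nested reading is the very one under which in-profile serious seizures go unrecorded, so it does not remove the problem.

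Second, keeping expected seizures out of the AE data is a sensible design choice, since they are already captured on the daily record card and the CRF as efficacy data. This stands for ordinary seizures. It gives no reason to leave out those that meet a seriousness criterion.

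Third, the CRF Completion Guidelines cited in 10.1.3 were not available and may settle the matter. If they do, the rule still belongs in the protocol, because it defines a primary variable.

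Fourth, there is no evidence that sites or regions actually differ, and the deleted background text shows convulsion recorded as a TEAE, as an SAE and as a reason for discontinuation in the earlier studies. That is true, but it does not show what was left out.

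A reader might also extend the point to withdrawal due to AE, since 6.3 lists "Withdrawal for safety reasons by the Investigator: occurrence of status epilepticus". Section 10.4 gives no support for this, as it concerns SAE reporting only. Section 6.3 lists lack or loss of efficacy as a separate reason, and SAP 5.1 tabulates discontinuation by primary reason from the termination CRF, so a seizure-driven withdrawal still appears in disposition even if the table of TEAEs leading to discontinuation misses it.

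**Conclusion.** The point holds as a gap in the recording rule. Section 10.1.1 has no exception for serious events and, read with 10.2.1 and 10.3, allows a seizure within the known profile that leads to admission or is life-threatening to be left out of the SAE data. Section 10.4 does not resolve it. Sites can differ, and a site following the literal text understates SAE occurrence.

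The size cannot be calculated. A reader might take 1.8 percentage points as the largest possible understatement, but it is not a bound. It is a rate of recorded events from superseded text on other studies, at a median exposure of 52 weeks, and their recording rule is not given. If they used the same restriction, the omitted events lie outside the 1.8%.

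The conclusion assumes that some serious seizures are judged to be within profile and that no guidance outside the two documents already covers them.

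**What to change.** **Protocol.** Reconcile 10.1.1 with 10.2.1 and 10.4 by adding to 10.1.1, for example: *This restriction does not apply to an event that meets any seriousness criterion in Section 10.2.1; such an event is recorded as an AE and as an SAE whatever the subject's history.* Repeat the rule in the CRF Completion Guidelines. It should not be extended to every seizure that leads to discontinuation, since that would turn lack-of-efficacy withdrawals into AE withdrawals.

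**Before database lock.** Match seizure-related hospitalizations against the SAE records, using hospital stays (9.1.5) for the first 2 years and medical procedures (9.1.3) for the whole study. Report the number of admissions without a matching SAE.

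**Cost.** One sentence and one reconciliation listing from data already collected. Procedures are not coded (SAP 3.7), so those entries need manual review. The reported SAE percentage may rise slightly and will include disease-related events; these remain visible because SAEs are already tabulated by preferred term, so no extra convulsion row is needed.

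**Limits.** Recruitment was planned from Q2 2011 and the SAP amendment is dated February 2019. For events already collected only the reconciliation helps, and it finds admissions, not life-threatening seizures managed without one. If the sentence takes effect during the study, the report should state the date, because the recording rule changes there.
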